8. MEASUREMENT OF EFFECT

The patients on this study will not have measurable disease at the time of radiation therapy. These patients will be followed for disease recurrence.

8.1 Antitumor Effect– Solid Tumors

8.1.1 Definitions

Evaluable for toxicity. All participants who receive at least one dose of study treatment will be evaluable for toxicity from the time of their first treatment.

Evaluable for response. Only those participants who have completed study treatment, and have had their disease re-evaluated will be considered evaluable for response. These participants will have their response classified according to the definitions stated below. (Note: Participants who exhibit objective disease progression or die prior to the end of study treatment will also be considered evaluable.

8.1.2 Progression-Free Survival

Tumor control is not the primary objective of this Pilot Study. Participants will be followed for toxicities and Progression-Free Survival (PFS), which is defined as the duration of time from start of treatment to time of objective disease progression.

Progressive disease will be defined as the appearance of one or more new lesions. Disease progression will be assessed at follow up by clinical exam, and may be further assessed by imaging as determined by the treating investigator.

9. ADVERSE EVENT REPORTING REQUIREMENTS

9.1 General

CONFIDENTIAL

This document is confidential. Do not disclose or use except as authorized.

Adverse event collection and reporting is a routine part of every clinical trial. This study will use the descriptions and grading scales found in the CTEP Active Version of the NCI Common Terminology Criteria for Adverse Events (CTCAE) will be utilized for AE reporting. The CTEP Active Version of the CTCAE is identified and located on the CTEP website at

http://ctep.cancer.gov/protocolDevelopment/electronic_applications/ctc.htm
<https://phsexchweb.partners.org/exchweb/bin/redir.asp?URL=http://ctep.cancer.gov/protocolDevelopment/electronic_applications/ctc.htm>. All appropriate treatment areas should have access to a copy of the CTEP Active Version of CTCAE.

Information on all adverse events, whether reported by the participant, directly observed, or detected by physical examination, laboratory test or other means, will be collected, recorded, followed and reported as described in the following sections.

Adverse events experienced by participants will be collected and reported from initiation of study treatment, throughout the study, and within 30 days of the last dose of study treatment. Participants who experience an ongoing adverse event or related to study procedures and/or study treatment beyond 30 days will continue to be contacted by a member of the study team until the event is resolved, stabilized, or determined to be irreversible by the participating investigator.

Participants should be instructed to report any serious post-study event(s) that might reasonably be related to participation in this study. The investigator should notify the IRB and any other applicable regulatory agency of any unanticipated death or adverse event occurring after a participant has discontinued or terminated study participation that may reasonably be related to the study.

9.2 Definitions

9.2.1 Adverse Event (AE)

An adverse event is any undesirable sign, symptom or medical condition or experience that develops or worsens in severity after starting the first dose of study treatment or any procedure specified in the protocol, even if the event is not considered to be related to the study.

Abnormal laboratory values or diagnostic test results constitute adverse events only if they induce clinical signs or symptoms or require treatment or further diagnostic tests.

9.2.2 Serious adverse event (SAE)

A serious adverse event is an undesirable sign, symptom, or medical condition which:

- is fatal or life-threatening;

CONFIDENTIAL

This document is confidential. Do not disclose or use except as authorized.

- requires or prolongs inpatient hospitalization;
- results in persistent or significant disability/incapacity;
- constitutes a congenital anomaly or birth defect; or
- jeopardizes the participant and requires medical or surgical intervention to prevent one of the outcomes listed above.

Events **not** considered to be serious adverse events are hospitalizations for:

- routine treatment or monitoring of the studied indication, not associated with any deterioration in condition, or for elective procedures
- elective or pre-planned treatment for a pre-existing condition that did not worsen
- emergency outpatient treatment for an event not fulfilling the serious criteria outlined above and not resulting in inpatient admission
- respite care

9.2.3 Expectedness

Adverse events can be 'Expected' or 'Unexpected.'

9.2.3.1 Expected adverse event

Expected adverse events are those that have been previously identified as resulting from administration of the agent. For the purposes of this study, an adverse event is considered expected when it appears in the current adverse event list, the Investigator's Brochure, the package insert or is included in the informed consent document as a potential risk.

Refer to Section 6.1 for a listing of expected adverse events associated with the study agent(s).

9.2.3.2 Unexpected adverse event

For the purposes of this study, an adverse event is considered unexpected when it varies in nature, intensity or frequency from information provided in the current adverse event list, the Investigator's Brochure, the package insert or when it is not included in the informed consent document as a potential risk.

9.2.4 Attribution

Attribution is the relationship between an adverse event or serious adverse event and the study treatment. Attribution will be assigned as follows:

- Definite – The AE is clearly related to the study treatment.

CONFIDENTIAL

This document is confidential. Do not disclose or use except as authorized.

- Probable – The AE is likely related to the study treatment.
- Possible – The AE may be related to the study treatment.
- Unlikely - The AE is doubtfully related to the study treatment.
- Unrelated - The AE is clearly NOT related to the study treatment.

9.3 Recording Adverse Events

Adverse event information will be obtained at each contact with the participant. All adverse events will be recorded on the appropriate study-specific case report forms (CRFs).

9.4 Reporting Adverse Events

Each adverse event will be assessed to determine if it meets the criteria for serious adverse event. If a serious adverse event occurs, expedited reporting will follow local policies, and federal guidelines and regulations as appropriate.

It is the responsibility of the participating investigator to notify the Principal Investigator (or Protocol Chair), IRB, and others of all serious adverse events as required in the protocol.

The Principal Investigator (or Protocol Chair) will provide information with respect to adverse events and safe use of the study treatment (e.g., safety reports, Action Letters) to all participating investigators as soon as the information becomes available.

9.5 Sponsor Notification by Investigator

9.5.1 Serious Adverse Event Reporting Requirements

All events meeting the criteria for Serious Adverse Event (see Section 11.2.2) that occur after the initial dose of study treatment, during treatment, or within 30 days of the last dose of treatment must be reported as serious adverse events.

The participating investigator must report each serious adverse event, regardless attribution, to the Principal Investigator (or Protocol Chair) within 24 hours of learning of the occurrence. In the event that the participating investigator does not become aware of the serious adverse event immediately (e.g., participant sought treatment elsewhere), the participating investigator is to report the event within 24 hours after learning of it and document the time of

CONFIDENTIAL

This document is confidential. Do not disclose or use except as authorized.

Eligibility Checklist	Complete prior to registration with QACT
On Study Form	Within 14 days of registration
Baseline Assessment Form	Within 14 days of registration
Treatment Form	Within 10 days of the last day of study treatment
Toxicity/Adverse Event Report Form	Weekly during study treatment; Within 10 days of protocol-defined follow up
Lab Form	Within 14 days of protocol required labs
Measurement/Response Form	Within 14 days of registration; within 10 days of protocol-defined follow up
Off Treatment/Off Study Form	Within 14 days of completing treatment or being taken off study for any reason
Follow up/Survival Form	Within 14 days of the protocol defined follow up visit date or call

10.2 Safety Meetings

The DF/HCC Data and Safety Monitoring Committee (DSMC) will review and monitor toxicity and accrual data from this trial. The committee is composed of clinical specialists with experience in oncology and who have no direct relationship with the study. Information that raises any questions about participant safety will be addressed with the Principal Investigator and study team.

The DSMC will meet as required to review toxicity and accrual data. Information to be provided to the committee may include: up-to-date participant accrual; current dose level information; DLT information; all grade 2 or higher unexpected adverse events that have been reported; summary of all deaths occurring within 30 days for Phase I or II protocols; for gene transfer protocols, summary of all deaths while being treated and during active follow-up; any response information; audit results, and a summary provided by the study team. Other information (e.g. scans, laboratory values) will be provided upon request.

10.3 Monitoring

CONFIDENTIAL

This document is confidential. Do not disclose or use except as authorized.

All data will be monitored for timeliness of submission, completeness, and adherence to protocol requirements. Monitoring will begin at the time of participant registration and will continue during protocol performance and completion.

11. REGULATORY CONSIDERATIONS

11.1 Protocol Review and Amendments

This protocol, the proposed informed consent and all forms of participant information related to the study (e.g., advertisements used to recruit participants) and any other necessary documents must be submitted, reviewed and approved by a properly constituted IRB governing each study location.

Any changes made to the protocol must be submitted as amendments and must be approved by the IRB prior to implementation. Any changes in study conduct must be reported to the IRB. The Principal Investigator (or Protocol Chair) will disseminate protocol amendment information to all participating investigators.

All decisions of the IRB concerning the conduct of the study must be made in writing.

CONFIDENTIAL

This document is confidential. Do not disclose or use except as authorized.

11.2 Informed Consent

All participants must be provided a consent form describing this study and providing sufficient information for participants to make an informed decision about their participation in this study. The formal consent of a participant, using the IRB approved consent form, must be obtained before the participant is involved in any study-related procedure. The consent form must be signed and dated by the participant or the participant's legally authorized representative, and by the person obtaining the consent. The participant must be given a copy of the signed and dated consent document. The original signed copy of the consent document must be retained in the medical record or research file.

11.3 Ethics and Good Clinical Practice (GCP)

This study is to be conducted according to the following considerations, which represent good and sound research practice:

- ICH Consolidated Good Clinical Practice: Guidelines (E6)
www.fda.gov/cder/guidance/iche6.htm
- US Code of Federal Regulations (CFR) governing clinical study conduct and ethical principles that have their origin in the Declaration of Helsinki
 - Title 21 Part 11 – Electronic Records; Electronic Signatures
www.access.gpo.gov/nara/cfr/waisidx_02/21cfr11_02.html
 - Title 21 Part 50 – Protection of Human Subjects
www.access.gpo.gov/nara/cfr/waisidx_02/21cfr50_02.html
 - Title 21 Part 54 – Financial Disclosure by Clinical Investigators
www.access.gpo.gov/nara/cfr/waisidx_02/21cfr54_02.html
 - Title 21 Part 56 – Institutional Review Boards
www.access.gpo.gov/nara/cfr/waisidx_02/21cfr56_02.html
 - Title 21 Part 312 – Investigational New Drug Application
www.access.gpo.gov/nara/cfr/waisidx_02/21cfr312_02.html
- State laws
- Institutional research policies and procedures
www.dfhec.harvard.edu/clinical-research-support/clinical-research-operations-cro/policies-and-procedures

CONFIDENTIAL

This document is confidential. Do not disclose or use except as authorized.

It is understood that deviations from the protocol should be avoided, except when necessary to eliminate an immediate hazard to a research participant. In such case, the deviation must be reported to the IRB according to the local reporting policy.

11.4 Study Documentation

The investigator must prepare and maintain adequate and accurate case histories designed to record all observations and other data pertinent to the study for each research participant. This information enables the study to be fully documented and the study data to be subsequently verified.

Original source documents supporting entries in the case report forms include but are not limited to hospital records, clinical charts, laboratory and pharmacy records, recorded data from automated instruments, microfiches, photographic negatives, microfilm or magnetic media, and/or x-rays.

11.5 Records Retention

All study-related documents must be retained for the maximum period required by applicable federal regulations and guidelines or institutional policies.

12. STATISTICAL CONSIDERATIONS

We propose to enroll a total of 96 patients in three cohorts following the study design indicated in 12.1 to evaluate independently the feasibility of intensity modulated proton therapy (IMPT) and 3D conformal protons following mastectomy or breast-conserving surgery. The separate cohorts will ensure adequate patient numbers for achieving reasonable precision in the assessment of acute, sub-acute and late toxicities associated with each proton technique in the specific population. The accrual goal includes 20% inflation to account for patients unevaluable or lost to follow-up so that adequate precision is maintained for longer-term endpoints. The target accrual has been adjusted based on the observed data among mastectomy patients with at least 6 months follow-up, including the completeness of strain echocardiogram testing.

12.1 Study Design/Endpoints

This is a pilot study substituting proton radiation for photon radiation, seeking to show the feasibility of proton radiation and to assess the rate of acute, sub-acute and late toxicities during and after proton radiation to the left chest wall and regional lymphatics. It is anticipated that patients undergoing proton radiation will not have increased toxicity compared to patients who have historically undergone photon radiation.

Proton radiation will be considered to be feasible as adjuvant treatment for invasive breast carcinoma in each cohort following surgery if the rate of grade 3 or higher radiation pneumonitis within 3 months of treatment were no more than 5%, within the range associated with conventional techniques of adjuvant radiation. In addition to radiation pneumonitis, the feasibility of proton radiation will also be compromised by any grade 4 effect occurring within 3 months of treatment, as well as skin toxicity and pericarditis. If 2 or more of the initial 12

CONFIDENTIAL

This document is confidential. Do not disclose or use except as authorized.

patients were to experience grade 3 or higher radiation pneumonitis or any grade 4 toxicity within 3 months of finishing radiation, accrual to a cohort will not continue further. The probability of stopping early is only 12% if the underlying rate of grade 3 or higher radiation pneumonitis or any grade 4 toxicity were truly 5%. Otherwise, the cohort will proceed to enroll a total of 26 patients and declare the feasibility of proton radiation if no more than 2 of them were to experience grade 3 or higher radiation pneumonitis or any grade 4 toxicity within 3 months after treatment. The two-stage design provides 81% power to accept that proton radiation is associated with a 5% rate of grade 3 or higher radiation pneumonitis or any grade 4 toxicity in a treated cohort. However, the probability is only 20% for declaring the feasibility of proton radiation if the underlying rate grade 3 or higher radiation pneumonitis or any grade 4 toxicity were truly 15%.

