6.3 Dose Modifications/Delays

Doses of radiation used are considered standard, i.e., this is not a dose escalation study, and interruption of radiation is not anticipated. Delays or interruptions of radiation therapy will be at the discretion of the treating physician, but the primary investigator should be notified if the number of days exceeds 3. Dose modifications for side effects should not be made without informing the primary investigator.

Proton radiation for invasive breast carcinoma will be considered to be feasible following surgery (mastectomy or breast-conserving) if the rate of grade 3 or higher radiation pneumonitis within 3 months of treatment were no more than 5%, within the range associated with conventional techniques of adjuvant radiation. In addition to radiation pneumonitis, the feasibility of proton radiation will also be compromised by any grade 4 effect occurring within 3 months of treatment, skin toxicity and pericarditis. If 2 or more

CONFIDENTIAL

This document is confidential. Do not disclose or use except as authorized.

of the initial 12 patients were to experience grade 3 or higher radiation pneumonitis or any grade 4 toxicity within 3 months of finishing radiation, accrual will not continue further. The probability of stopping early is only 12% if the underlying rate of grade 3 or higher radiation pneumonitis or any grade 4 toxicity were truly 5%. Otherwise, the protocol will proceed to enroll a total of 26 patients and declare the feasibility of proton radiation if no more than 3 of them were to experience grade 3 or higher radiation pneumonitis or any grade 4 toxicity within 3 months after treatment.

CONFIDENTIAL

This document is confidential. Do not disclose or use except as authorized.

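### After stage 1 a cohort has no further accrual boundary, so it is still directed to 26 patients (32 with inflation) once its event count rules out a feasibility declaration

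*Combined protocol and SAP*

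**What the plan says.** Section 12.1 sets one accrual boundary for each cohort. It begins "If 2 or more of the initial 12" patients, the event being grade 3 or higher radiation pneumonitis or any grade 4 toxicity within 3 months of finishing radiation. If that count is reached, "accrual to a cohort will not continue further". For a cohort below it, the instruction is "Otherwise, the cohort will proceed to enroll a total of 26 patients and declare the feasibility of proton radiation if no more than 2" have an event. No look, pause or boundary is given after patient 12.

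Section 6.3 has the same structure ("Otherwise, the protocol will proceed to enroll a total of 26 patients"), but its final limit is no more than 3 events, not 2.

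Section 12 sets total accrual at 96 in three cohorts, including 20% inflation for unevaluable or lost patients, so that precision for longer-term endpoints is kept. Section 12.1.1 gives 32 for the intact-breast cohort and 64 for the post-mastectomy patients.

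Section 10.2 has the DSMC review toxicity and accrual, meeting as required. The material it may receive includes "all grade 2 or higher unexpected adverse events that have been reported", deaths within 30 days, dose-limiting toxicity information and a study-team summary. No count of the events that drive the Section 12.1 rule is named, and no number is tied to the review.

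**The concern.** The final limit is a toxicity limit. A cohort with 0 or 1 events in its first 12 patients can pass that limit well before patient 26. From then on the primary conclusion for the cohort cannot change, but the text still directs enrolment. The patients enrolled after that point carry the risk that the limit was set to control.

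The reporting routes do not clearly make up for this. Serious adverse events go to the Principal Investigator up to 30 days after the last dose (Section 9.5.1), whereas qualifying events count to 3 months. Pneumonitis is on the list in Section 6.1 that Section 9.2.3.1 uses to define expected events, while the adverse-event item named for the DSMC is limited to unexpected ones. Section 6 does collect radiation-related events of grade 2 or more throughout the study, so the data will exist. What the plan lacks is a written duty to count them by cohort and act on the count.

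**Working it through.** **Inputs.** Stage 1: 12 patients, stop at 2 or more events. Final: 26 patients, feasible with 2 or fewer (Section 12.1) or 3 or fewer (Section 6.3). True rates of 5% and 15% (Section 12.1). Accrual of about 15 per year post-mastectomy, and 32 in 5-6 months for intact breast (Section 12.1.1). Patients are taken as independent.

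**1. The plan's own figures.** The claims are "The probability of stopping early is only 12% if the underlying rate of grade 3 or higher radiation pneumonitis or any grade 4 toxicity" is 5%; "The two-stage design provides 81% power to accept that proton radiation is associated with a 5% rate"; and, at 15%, "the probability is only 20% for declaring the feasibility of proton radiation".

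- P(early stop) = 1 − P(0 of 12) − P(1 of 12). At 5%: 1 − 0.5404 − 0.3413 = 0.118 (stated 12%).
- P(feasible) = P(0 of 12) × P(≤2 of 14) + P(1 of 12) × P(≤1 of 14).
- At 5%: 0.5404 × 0.9699 + 0.3413 × 0.8470 = 0.813 (stated 81%).
- At 15%: 0.1422 × 0.6479 + 0.3012 × 0.3567 = 0.200 (stated 20%).

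All three reproduce with the limit of 2. With the Section 6.3 limit of 3, P(feasible) is 0.869 at 5% and 0.317 at 15%, which do not match. On the design as calculated, the third event is the decisive one.

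**2. How often a cohort passes stage 1 and then exceeds the limit.** This is P(pass stage 1) − P(feasible).

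- At 15%: 0.4435 − 0.1996 = 0.244 of all cohorts, or 0.244/0.4435 = 55% of those that pass stage 1.
- At 5%: 0.8816 − 0.8132 = 0.068 of all cohorts.

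**3. Patients enrolled after that point.** The third event falls at patient k (13 to 26) with probability p × [P(0 of 12) × P(2 of k−13) + P(1 of 12) × P(1 of k−13)]. If L further patients enrol before the event is known, a hold saves max(0, N − k − L) patients, where N is 26 or 32. The 3-month window at 15 per year gives 15 × 3/12 = 3.75, so L = 4. This is an assumption: events may be known sooner, and time on treatment adds to the delay.

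| True rate | Lag | Mean saved in affected cohorts, to 26 / to 32 | Mean saved per cohort opened, to 26 / to 32 |
|---|---|---|---|
| 15% | 0 | 5.4 / 11.4 | 1.3 / 2.8 |
| 15% | 4 | 2.2 / 7.4 | 0.5 / 1.8 |
| 5% | 4 | 1.4 / 6.2 | 0.1 / 0.4 |

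The affected cohorts are those with a third event by patient 26. The figures to 32 assume that all six inflation patients enrol after the 26. In the extreme case the third event is patient 14, leaving 12 more to reach 26 and 18 more to reach 32.

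**4. Intact-breast cohort.** At 32 in 5-6 months, a 3-month window takes in 32 × 3/6 = 16 to 32 × 3/5 = 19 patients. Even at L = 16 the saving to 26 is zero, since 26 − 14 − 16 is negative. To 32 it averages 0.03 per cohort opened at a 15% rate.

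**5. Effect of a hold on the decision.** Three events cannot become two. P(feasible) stays at 81.3% and 20.0%, and the early-stop probability is untouched.

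**6. Cost in precision.** The maximum half-width of the exact 95% interval is 20% at 26 patients (as Section 12.2.1 states) and 27% at 14.

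**The case against.** The strongest reply is that this is an ordinary two-stage design. Its figures are right, and full enrolment has a stated purpose: Section 12 ties cohort size to precision for acute, sub-acute and late toxicity, and Section 12.2.1 bases its half-width on 26 patients. An automatic permanent stop would cost precision in the cohort where toxicity matters most. It would also leave an observed rate biased upward by stopping on an event. This stands, and it is why a hold with review suits the plan better than a fixed stop. The plan does not, however, say that it means to continue past a failed limit for precision.

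A reader might also infer that the DSMC could not notice a third event. The documents do not support that. The list in Section 10.2 is permissive and includes a study-team summary, with other information on request. Section 9.2.3.2 lets an event count as unexpected through its intensity or frequency, so repeated grade 3 pneumonitis could qualify. Section 5.6 requires immediate notice to the Principal Investigator of life-threatening complications. What can be said is that no running count is required.

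Finally, little may be left to save. Section 12.1.1 projects another 4-5 months to move the post-mastectomy goal from 58 to 64, which suggests that those cohorts are nearly full, although no enrolled count is given. This limits the practical gain but leaves the gap in the text.

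**Conclusion.** The point holds as a cheap safety improvement. It would be wrong to read it as an error in the sample size or operating characteristics, because every stated probability reproduces. It would also be too strong to say that the plan has classed the technique as not feasible at the third event. The declaration is made on the 26-patient result, and the third event only makes a favourable one impossible.

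The size is modest. The means in affected cohorts are conditional on failure and on a poor true rate, so the fairer summary at 15% is about half a patient per cohort opened on the 26-patient plan and just under two on the 32-patient plan. At 5% the saving is negligible. The result rests on independent events, a 4-patient lag and the Section 12.1 limit. Under Section 6.3 the fourth event would be decisive, and the documents must settle which applies. The main value lies in a written rule and a mandated count.

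**What to change.** 1. Reconcile the final limit in Section 6.3 with Section 12.1, and show that the chosen limit matches the quoted 81% and 20%.
2. Add to both sections, for example: *After stage 1, once the number of patients in a cohort with a qualifying event exceeds the final limit, feasibility can no longer be declared for that cohort. Accrual to it is suspended pending DSMC review, and resumes only if the DSMC agrees that further enrolment for the descriptive toxicity endpoints is justified.*
3. Add to Section 10.2 that each qualifying event up to 3 months after radiation, expected or not, is reported to the DSMC with the running count for that cohort.
4. State that the event rate from a cohort closed this way will be reported as coming from an event-triggered stop.

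The cost is a few sentences and some reporting work. The stated 12%, 81% and 20% need no revision if the Section 12.1 limit is kept. A failed cohort that does not resume gives wider intervals for the secondary endpoints, with a maximum half-width of 27% if it ends at 14 patients against 20% at 26.

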12.1.1 Sample Size/Accrual Rate

We estimate an annual enrollment of 16-20 patients based on the existing referral patterns and proton slot availability over 3 years of active accrual. Since protocol enrollment began in August 2011, the accrual rate has been about 15 patients per year, thus increasing the accrual goal from 58 to 64 post-mastectomy patients is projected to take another 4-5 months. Based on existing referral patterns of patients following breast-conserving surgery, we estimate the intact breast cohort will require 5-6 months to enroll the cohort goal of 32 patients. All patients will be followed for an additional 5 years to allow for the assessment of late toxicities and progression-free survival.

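### The feasibility rule and its 81%/20% operating characteristics are set on 26 patients per cohort, accrual is about 32, and no text says which patients decide

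*Combined protocol and SAP*

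**What the plan says.** Section 12.1 sets a two-stage rule for each cohort. Accrual stops if 2 or more of the first 12 patients have a qualifying toxicity (pneumonitis of grade 3 or above, or any grade 4 event, within 3 months of radiation). Otherwise "the cohort will proceed to enroll a total of 26 patients", and feasibility is declared if at most 2 of them have such an event. The section gives a 12% chance of early stopping and 81% power at a true rate of 5%, and a 20% chance of declaring feasibility at 15%. Section 12.2.1 also uses 26 as the sample size for precision.

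The accrual figures are larger. Section 12: "We propose to enroll a total of 96 patients in three cohorts following the study design indicated in 12.1". Section 12.1.1 speaks of "increasing the accrual goal from 58 to 64 post-mastectomy patients" and of "5-6 months to enroll the cohort goal of 32 patients" for the intact-breast group. Section 12 gives the reason: "The accrual goal includes 20% inflation to account for patients unevaluable or lost to follow-up so that adequate precision is maintained for longer-term endpoints".

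On evaluability, Section 8.1.1 says: "All participants who receive at least one dose of study treatment will be evaluable for toxicity from the time of their first treatment". Item 12.5.1, printed under Section 12.3, says the same in substance.

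**The concern.** The inflation is there for late endpoints, but the primary endpoint is read at 3 months. Because evaluability for toxicity starts at first treatment, few patients are likely to drop out of the toxicity denominator, and more than 26 per cohort can have a 3-month result. The protocol does not say whether events in patients 27 to 32 count towards feasibility, or what threshold applies above 26. It also states two enrolment totals for the same cohort.

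The primary conclusion of each cohort is at stake. Two analysts following the text in good faith could use different denominators and, in some cohorts, reach opposite conclusions. The quoted 81% and 20% describe only one of those readings.

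**Working it through.** **Inputs.** Look at 12 patients, stop at 2 or more; final n = 26; threshold at most 2; true rates 5% and 15% (all Section 12.1). Accrual 96 = 64 + 32 (Sections 12 and 12.1.1). The 32 is stated for the intact-breast cohort. For each post-mastectomy cohort, 64/2 = 32 assumes an equal split.

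**Link between 26 and 32.** 26 × 1.2 = 31.2, rounded up to 32. So 32 is 26 with the stated inflation.

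**Formula.** A cohort continues only with 0 or 1 event in 12. For final size n and threshold a,

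P(feasible) = P(X₁=0)·P(Y ≤ a) + P(X₁=1)·P(Y ≤ a−1), with X₁ ~ Bin(12, p) and Y ~ Bin(n−12, p).

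At p = 5%, P(X₁=0) = 0.5404 and P(X₁=1) = 0.3413. At p = 15% they are 0.1422 and 0.3012.

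**The plan's own figures (at most 2 of 26).**
- Early stop at 5%: 1 − 0.5404 − 0.3413 = 11.8% (stated 12%).
- At 5%: 0.5404 × 0.9699 + 0.3413 × 0.8470 = 0.8132 (stated 81%).
- At 15%: 0.1422 × 0.6479 + 0.3012 × 0.3567 = 0.1996 (stated 20%).

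All three reproduce.

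**Same threshold on all 32.**
- At 5%: 0.5404 × 0.9245 + 0.3413 × 0.7358 = 0.7507.
- At 15%: 0.1422 × 0.4049 + 0.3012 × 0.1756 = 0.1105 (0.11047 before rounding the terms, so 11.0%).

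**Summary of P(feasible), 12-patient look kept.**

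| Final rule | True rate 5% | True rate 15% |
|---|---|---|
| at most 2 of 26 (Section 12.1) | 81.3% | 20.0% |
| at most 2 of 27 | 80.4% | 18.2% |
| at most 2 of 31 | 76.2% | 12.3% |
| at most 2 of 32 | 75.1% | 11.0% |
| at most 3 of 32 (not in the plan) | 84.7% | 21.4% |
| at most 3 of 26 (Section 6.3) | 86.9% | 31.7% |

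**How often the reading changes the answer.** With the threshold held at 2, a cohort that passes on all 32 must also pass on its first 26. The readings therefore disagree exactly when the cohort passes on 26 and fails on 32, and the probability is the difference between the two rows:
- at 5%: 0.81319 − 0.75070 = 0.0625 (0.06249, so 6.2%);
- at 15%: 0.1996 − 0.1105 = 0.0891, or 8.9%.

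**The case against.** The strongest reply is that the ordinary reading is already clear: a decision on 26, with the surplus held for late endpoints. Section 12 says the 96 are enrolled under the Section 12.1 design, the inflation is explained, and Section 12.2.1 works with 26. That is the natural reading, and under it the stated error rates stand. It remains an inference, however. Section 12.1 still says the cohort enrols 26, and no sentence separates the deciding patients from the rest.

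Several stronger readings are tempting, and the documents do not support them.

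- A reader might infer that there is no valid primary rule. There is one, and it reproduces to the stated precision.
- A reader might infer that choosing between 26 and 32 after seeing the events inflates false feasibility. Under the single threshold in Section 12.1 it cannot: the more favourable choice is always the first-26 answer, so the probability at a 15% rate stays at 20.0%. The cost of the ambiguity is power.
- A reader might infer that a patient lost in the second week is scored event-free. Sections 8.1.1 and 12.5.1 say when evaluability begins. They do not say how early loss is scored.
- A reader might suspect that the accrual change was driven by toxicity results. Section 12 says it rests on observed data in mastectomy patients, "including the completeness of strain echocardiogram testing". It does not mention primary-event counts.

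The documents also do not show how the trial was conducted, so this is a point about the written plan only.

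**Conclusion.** The concern holds as a conflict over sample size and decision set, of moderate size. The plan gives two enrolment totals per cohort and does not name the patients who decide the primary endpoint once more than 26 are assessable. If the threshold of 2 is applied to all 32, power falls from 81.3% to 75.1% and false feasibility from 20.0% to 11.0%. The answer differs between readings in 6.2% of cohorts at a true rate of 5% and 8.9% at 15%.

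These figures assume independent patients with a common event rate, all 32 assessable at 3 months, the 12-patient look applied as written, and, for the post-mastectomy cohorts, an equal split of 64. With 27 to 31 assessable, the results lie between the two readings.

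**What to change.** Amend Section 12.1 in two places.

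1. Replace the enrolment figure of 26 with the accrual goal for the cohort.
2. State the decision set. Suggested wording: 'The feasibility decision in each cohort uses the first 26 treated patients, in order of registration, who have a qualifying event or have been followed to 3 months after radiation. A patient lost earlier without an event is replaced in this set by the next patient. Later patients contribute to secondary endpoints. The event rate in all treated patients is reported with an exact 95% confidence interval beside the decision.'

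The 12-patient look should follow the same ordering. The text should also say what record establishes follow-up to 3 months, because the Section 7 calendar goes from a 2-month visit to a 6-month visit.

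If the sponsor prefers to decide on all 32, the operating characteristics must be restated for the threshold chosen: 75%/11% for at most 2 of 32, or 85%/21% for at most 3 of 32. The latter exceeds the plan's own 20%.

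Section 6.3 gives a final threshold of 3 of 26 where Section 12.1 gives 2 of 26. The stated 81%/20% matches only the latter; the former gives 86.9%/31.7%. The two sections must be reconciled in the same amendment.

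The cost is a protocol wording amendment, which Section 11.1 sends to the IRB for approval. No extra patients are needed.
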